**Date of document: (Version 3 13/04/2018)**

### Clinical hypothesis

The primary hypothesis is that increased mean radiation dose to the teeth and to the 'spared' parotid gland is associated with an increase in the mean number of carious teeth and in the proportion with periodontal disease 2 years post-radiotherapy.

### **Study design: Prospective cohort study.**

- Pre-radiotherapy assessment at baseline and patients rendered dentally fit (i.e. free of dental disease).
- Post-radiotherapy follow-up assessments at 6 months, 12 months, and 24 months.

**Selection criteria:** Adult dentate patients (i.e. patients with natural teeth) diagnosed with a primary or secondary malignant tumour of the oral cavity, nasal cavity, sinuses, salivary glands, pharynx, or larynx\* requiring radiation treatment within Northern Ireland. \*International Classification of Diseases (ICD-10) codes C00.0-C14.8 and C30.0-32.9.

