### Clinical assessment

**-Dental caries:** The presence or absence of dental caries on each tooth will be determined using the World Health Organization's criteria and coding system, and ICDAS, and recorded in a modified version of the Oral Health Assessment Form for Adults, 2013. All surfaces of the crown and root of each tooth will be assessed by: visualisation using a mouth mirror, dental probe, adequate lighting, and compressed air from a 3-in-1 tip.

Presence or absence of dental caries on each surface will be recorded as follows (Figures 1 and 2):

Code		Condition/status	
Primary teeth	Permanent teeth	Crown	Root
A	0	0	Sound
B	1	1	Caries
C	2	2	Filled, with caries
D	3	3	Filled, no caries
E	4	—	Missing due to caries
—	5	—	Missing for any other reason
F	6	—	Fissure sealant
G	7	7	Fixed dental prosthesis abutment, special crown or veneer/implant
—	8	8	Unerupted tooth (crown)/unexposed root
—	9	9	Not recorded

Figure 1: WHO criteria and coding system

[figure not shown]

Figure 2: ICDAS coronal caries decision tree

**-Periodontal disease:** A six-point periodontal charting will be performed for all patients. Clinical attachment loss and probing pocket depths will be measured using a Williams Periodontal Probe and recorded for six sites on each tooth using the Oral Health Assessment Form. The 'Centers for Disease Control and Prevention (CDC)', in partnership with the 'American Academy of Periodontology (AAP)' workgroup definition of periodontitis will be used to identify those with active periodontal disease: 2 or more interproximal sites with attachment loss  $\geq 3$  mm, and 2 or more interproximal sites with pocket depths  $\geq 4$  mm (not on same tooth) or one site with pocket depth  $\geq 5$  mm.

**-Stimulated salivary flow rate** using paraffin pellets. Patients will chew an unflavoured paraffin pellet for 5 minutes whilst expectorating into a pre-weighed disposable specimen pot. This will be undertaken in one of the private units in the Prosthetics Department of the School of Dentistry, Belfast. Following collection, the specimen pot will be transported to the Institute of Pathology, Royal Victoria Hospital, Belfast. The mass of collected saliva will be determined using a calibrated precision weighing balance. After the calculation of salivary flow rate, each patient's saliva sample will be disposed of as clinical waste and destroyed by incineration in line with the Human Tissue Act 2004.

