### Denture hygiene instruction

- Don't wear dentures during the course of radiotherapy if possible
- Rinse dentures after every meal in cold running water
- Clean dentures at least once daily with a toothbrush and 5,000 ppm Duraphat fluoride toothpaste
- Soak in Milton's (1 in 80 dilution) overnight if the denture is made of plastic only
- Alternatively, soak in Corsodyl (chlorhexidine gluconate) 0.2% overnight if the denture has metal components

A dental treatment plan will be formulated for each patient to ensure adequate dental fitness prior to radiotherapy. Consultants in Restorative Dentistry, will oversee patients' treatment plans. Dental treatment required pre-radiotherapy (e.g. restorations and extractions) will be co-ordinated by the School of Dentistry in line with current practice, including the possibility of routine treatment within the primary care setting (i.e. completed by the patient's general dental practitioner).

To facilitate the micro-costings study, all patients will be asked to retain details of any treatment costs that they incurred from their general dental practice. Patients will be asked to provide this cost information at follow-up appointments (for example, with the production of invoices). Information on the cost of dental treatment incurred will be recorded on each patient's anonymised questionnaire booklet completed at the subsequent follow-up appointment.

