## 2. Dental restorations (“fillings”)

**Permanent restorations should be undertaken where possible.**

**Minimum** = Render tooth caries-free (including crown removal where appropriate) and adequate temporization (e.g. with glass ionomer restoration).

**Minimum when a tooth has been diagnosed with pulpal/apical pathology** = 1st stage RCT and adequate temporization (e.g. with glass ionomer restoration).

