## **Protocol for post radiotherapy dental assessments**

Participants will be followed-up at 6 months, 12 months, and 24 months post-radiotherapy.

Patients will undergo dental assessment on a Wednesday morning or afternoon in the Prosthetics Department of the School of Dentistry, Belfast. The following measurements will be collected (using the same methods and examiners outlined above): charting of dental caries, 6-point clinical attachment loss and probing pocket depth charting, stimulated salivary flow rate, mouth opening, oral hygiene practice, dietary assessment, quality of life, patient reported xerostomia, micro-costings study.

N.B. – For each patient, all efforts must be made to ensure that saliva collection is undertaken at a similar time of day for each of the four dental assessment appointments (i.e. the pre-radiotherapy assessment appointment and the three post-radiotherapy assessment appointments). This is due to the diurnal variation in saliva production. Patients will be asked to refrain from smoking, eating and drinking, and other forms of oral stimulation (e.g. oral hygiene) 90 minutes prior to the collection of saliva at post-radiotherapy assessment appointments. These instructions will be explained and provided in writing, and attached with the post-radiotherapy assessment appointment letter as a reminder to patients.

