## **Statistical analysis**

Primary outcome measures to be analysed include: (1) the number of carious teeth and (2) the presence of periodontal disease.

(1) Initial comparisons between the radiation dose to the 'spared' parotid gland and the number of carious teeth will be performed using independent t-tests (categorising radiation dose as <20Gy and >20Gy) and ANOVA (categorising radiation dose as <20Gy, 20-30Gy, 30-40Gy, and >40Gy) as appropriate. Adjusted analysis will be performed using multiple linear regression, with the number of carious teeth as the outcome variable, radiation dose to the 'spared' parotid gland as an explanatory variable

(categorised as above) along with potential confounding variables: dental radiation dose, oral hygiene practice, diet, and mouth opening. Without categorising radiation dose, a separate analysis will be conducted using linear regression with the number of carious teeth as the outcome variable and radiation dose to the 'spared' parotid gland (Gy) as the explanatory variable to give the increase in the number of carious teeth per 10 unit increase in Gray. If the number of carious teeth is not normally distributed transformations will be used prior to analysis or equivalent non-parametric techniques will be used.

(2) Initial comparisons of the association between radiation dose to the 'spared' parotid gland (categorised as above) and the presence of periodontal disease (Yes/No) will be performed using chi-square tests. Adjusted analysis will be performed using logistic regression with presence of periodontal disease as the outcome variable, radiation dose to the 'spared' parotid gland as the explanatory variable and dental radiation dose, oral hygiene practice, diet, smoking, medical history, and mouth opening as potential confounders.

Similar analyses will be undertaken to determine the effects of dental radiation dose and tumour location on the number of carious teeth and the presence of periodontal disease in post-radiotherapy head and neck cancer patients.

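### The adjusted model for the primary caries outcome has no term for baseline caries, although caries is charted on every tooth before radiotherapy

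*Combined protocol and SAP*

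**What the plan says.** The design section (Study design) sets the starting state as "Pre-radiotherapy assessment at baseline and patients rendered dentally fit (i.e. free of dental disease".

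Baseline caries is collected in full. Under Clinical assessment, "The presence or absence of dental caries on each tooth will be determined using the World Health Organization's criteria and coding system, and ICDAS", covering all crown and root surfaces. The pre-radiotherapy Radiographs section adds a mandatory panoramic film and has radiographic caries recorded on the same form.

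Treatment follows that charting: "A dental treatment plan will be formulated for each patient to ensure adequate dental fitness prior to radiotherapy". It may be done outside the study team, "including the possibility of routine treatment within the primary care setting (i.e. completed by the patient's general dental practitioner". The section on dental restorations prefers permanent restorations and sets as its minimum "Render tooth caries-free (including crown removal where appropriate) and adequate temporization".

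The study has four assessments: "the pre-radiotherapy assessment appointment and the three post-radiotherapy assessment appointments". The last three are at 6, 12 and 24 months, and the section on prevention and treatment planning after radiotherapy provides for treatment plans to restore dental health.

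The Statistical analysis section names the number of carious teeth as a primary outcome, without restricting it to new lesions. The adjusted linear model contains parotid dose and "potential confounding variables: dental radiation dose, oral hygiene practice, diet, and mouth opening". Similar analyses are planned for dental dose and tumour location. The next paragraph, on secondary outcomes, uses ANCOVA for variables measured at baseline and adds the baseline value to the adjusted models. No such provision is made for the primary caries count.

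**The concern.** This is an observational dose-response study, so nothing in the design balances prior caries risk across levels of dose or across tumour sites. A patient with many carious teeth at presentation may still be at high risk after those teeth are filled or extracted. Oral hygiene practice and diet, both taken from a questionnaire, capture part of that risk. The most direct measure, the caries chart made before radiotherapy, is left out of the model.

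Two consequences follow, depending on a fact the documents do not give. If baseline caries is related to dose or to tumour site, which is itself analysed as an exposure, the adjusted estimate remains confounded. If it is unrelated to dose, the estimate is not biased on that account, but variation that could be explained goes into the residual error.

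A secondary matter is that no study chart is made between the end of dental treatment and radiotherapy. The caries-free start is therefore intended but not confirmed by an examiner, and the outcome as defined does not separate an old lesion from a new one.

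**Working it through.** **Inputs from the Sample size section.** SD 4.0 carious teeth; 80%/20% split; difference 3.0; 150 evaluable patients; correlation target r = 0.22; 5% level (taken as two-sided); 30% dropout.

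**Assumed input.** The correlation ρ between the baseline and 24-month caries counts is not in the documents. I use 0.3 to 0.5, with baseline caries unrelated to dose.

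**1. The plan's own figures**
- Group comparison, 30 against 120: SE = 4.0 × √(1/30 + 1/120) = 0.816. Then 3.0/0.816 = 3.67, and 3.67 − 1.96 = 1.71, so power is 95.7% (95.5% by the noncentral t). This agrees with the stated figure of over 80%.
- Correlation, Fisher z: atanh(0.22) × √147 = 0.2237 × 12.12 = 2.71, and 2.71 − 1.96 = 0.75, so power is 77.4%. The regression t-test gives 78.4%. Both are slightly under the stated 80%.
- Recruitment: 150/0.70 = 214.3, rounded up to 215, as stated.

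The group comparison has ample slack. The correlation target has none.

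**2. Effect of adding baseline caries (residual variance × (1 − ρ²))**

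| ρ | Variance removed | Residual SD | Equivalent N, 150/(1 − ρ²) | Power, difference 3.0 |
|---|---|---|---|---|
| 0 | 0% | 4.00 | 150 | 95.7% |
| 0.3 | 9% | 3.82 | 165 | 97.1% |
| 0.5 | 25% | 3.46 | 200 | 98.9% |

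For the correlation target, the partial correlation is 0.22/√(1 − ρ²), tested with one further degree of freedom spent:

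| ρ | Partial r | Fisher z: atanh × √146 − 1.96 | Power (Fisher z) | Power (regression t) |
|---|---|---|---|---|
| 0.3 | 0.231 | 2.84 − 1.96 = 0.88 | 81.0% | 82.2% |
| 0.5 | 0.254 | 3.14 − 1.96 = 1.18 | 88.1% | 89.2% |

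The regression on continuous parotid dose is written with dose as its only explanatory variable. This gain therefore reaches the r = 0.22 target only if baseline caries enters that regression too.

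**3. Carry-over, illustration only**

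Suppose untreated lesions differed between the dose groups by a given mean number of teeth, all persisted to 24 months, and dose had no true effect. With SE 0.816 the unadjusted 5% test would reject as follows:

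| Difference in carry-over (teeth) | Rejection rate |
|---|---|
| 0.25 | 6.1% |
| 0.5 | 9.4% |
| 1.0 | 23.2% |

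The documents give no basis for choosing among these values. If carry-over were unrelated to dose and only added an SD of 1 or 2 teeth, the difference would be unbiased and power would fall to 94.6% or 90.8%.

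**The case against.** The strongest case against is that the plan already deals with prior caries. Every patient is to be made free of disease, so a baseline count may predict little at 24 months. Oral hygiene and diet are in the model. The group comparison has about 96% power without help. No passage links caries to dose, and the oncologist plans radiotherapy independently of the study.

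Much of this stands. Confounding is conditional, and the gain for the group comparison is small. It does not explain why a variable charted on every tooth is left out of the primary model when baseline adjustment is used for secondary outcomes. Nor does it help the correlation target, which falls just short of its stated power.

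A reader might infer something stronger: that baseline caries is not recorded, or that part of the 24-month count is disease from before radiotherapy. The documents support neither reading.
- Baseline caries is charted in full; only the state after dental treatment is not.
- The restoration minimum is removal of caries as well as a temporary filling, so a lesion left in place would depart from the plan.
- The hypothesis concerns 2 years. A lesion from before radiotherapy would have to be missed or left untreated before radiotherapy and again after the 6- and 12-month charts.
- Carry-over biases the dose effect only if it differs by dose.
- Caries that recurs in a tooth cleared before radiotherapy is arguably part of the outcome of interest, not a leftover.

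**Conclusion.** The omission of baseline caries from the adjusted primary caries model is plain in the text and worth correcting before analysis. It is an improvement available from data already planned, not a demonstrated flaw in the primary result. The precision gain, 9 to 25% of residual variance and correlation power of 81 to 89% instead of 77 to 78%, rests on the assumed ρ of 0.3 to 0.5 and on baseline caries being unrelated to dose. If baseline caries is related to dose, the benefit is less confounding, and its size cannot be given from the documents. The sample size need not rise. Carry-over of untreated lesions remains possible, unconfirmed, and limited by treatment planned during follow-up.

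**What to change.** 1. In the Statistical analysis section, add the baseline number of carious teeth (or baseline caries experience from the same chart) as a covariate in the adjusted caries models for parotid dose, dental dose and tumour location. State whether the regression on continuous parotid dose will also include it; the power gain above depends on that.
2. Add a sensitivity analysis that excludes, or reports separately, teeth carious at baseline with no recorded treatment before radiotherapy. Use the existing charts, dental notes and practitioner reports. Teeth treated before radiotherapy stay in the count, so recurrence in them is still counted as an outcome.

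The cost is SAP wording, one covariate, and some effort to trace treatment records. Practitioners are asked to report treatment they carry out, so a missing record may mean missing information and not an untreated tooth; for that reason item 2 should remain a sensitivity analysis. No new visit, change in care or larger sample is needed.

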### Exclusion criteria:

- Patients deemed to have poor prognosis, or patients to receive palliative treatment only (as advised by the Clinical Oncology team).
- Patients with less than 6 teeth before the radiotherapy start date.
- Patients with recurrent head and neck cancer, or patients receiving a repeat course of head and neck radiotherapy.
- Patients with diseases affecting tooth development (e.g. amelogenesis or dentinogenesis imperfecta) or salivary gland function (e.g. Sjogren's Syndrome).
- Patients with pre-existing trismus (mouth opening less than 35mm).

## **Protocol for pre-radiotherapy dental assessment**

In line with current practice, the Multidisciplinary Head and Neck Cancer Team (Royal Victoria Hospital, Belfast) will continue to refer head and neck cancer patients for pre-radiotherapy dental assessment to the School of Dentistry, Belfast. Referred patients will be assessed in the existing 'Head and Neck Clinic' on a Wednesday morning or afternoon in the Prosthetics Department of the School of Dentistry, Belfast, as per current clinical practice.

All potentially eligible patients will be informed of the research study and invited to participate. Willing participants will be asked to sign a written consent form. A member of the direct care team – a dentist – will complete all of this process.

Each recruited patient will be assessed by a trained and calibrated dentist (examiner). Examiners will undergo pre-study training and calibration to ensure consistent clinical measurements. Inter-examiner consistency will be calculated using the Kappa statistic. The same examiner(s) will also interpret and record data from all prescribed radiographs.

### Clinical assessment

**-Dental caries:** The presence or absence of dental caries on each tooth will be determined using the World Health Organization's criteria and coding system, and ICDAS, and recorded in a modified version of the Oral Health Assessment Form for Adults, 2013. All surfaces of the crown and root of each tooth will be assessed by: visualisation using a mouth mirror, dental probe, adequate lighting, and compressed air from a 3-in-1 tip.

Presence or absence of dental caries on each surface will be recorded as follows (Figures 1 and 2):

Code		Condition/status	
Primary teeth	Permanent teeth	Crown	Root
A	0	0	Sound
B	1	1	Caries
C	2	2	Filled, with caries
D	3	3	Filled, no caries
E	4	—	Missing due to caries
—	5	—	Missing for any other reason
F	6	—	Fissure sealant
G	7	7	Fixed dental prosthesis abutment, special crown or veneer/implant
—	8	8	Unerupted tooth (crown)/unexposed root
—	9	9	Not recorded

Figure 1: WHO criteria and coding system

[figure not shown]

Figure 2: ICDAS coronal caries decision tree

**-Periodontal disease:** A six-point periodontal charting will be performed for all patients. Clinical attachment loss and probing pocket depths will be measured using a Williams Periodontal Probe and recorded for six sites on each tooth using the Oral Health Assessment Form. The 'Centers for Disease Control and Prevention (CDC)', in partnership with the 'American Academy of Periodontology (AAP)' workgroup definition of periodontitis will be used to identify those with active periodontal disease: 2 or more interproximal sites with attachment loss  $\geq 3$  mm, and 2 or more interproximal sites with pocket depths  $\geq 4$  mm (not on same tooth) or one site with pocket depth  $\geq 5$  mm.

**-Stimulated salivary flow rate** using paraffin pellets. Patients will chew an unflavoured paraffin pellet for 5 minutes whilst expectorating into a pre-weighed disposable specimen pot. This will be undertaken in one of the private units in the Prosthetics Department of the School of Dentistry, Belfast. Following collection, the specimen pot will be transported to the Institute of Pathology, Royal Victoria Hospital, Belfast. The mass of collected saliva will be determined using a calibrated precision weighing balance. After the calculation of salivary flow rate, each patient's saliva sample will be disposed of as clinical waste and destroyed by incineration in line with the Human Tissue Act 2004.

Patients will be asked to refrain from smoking, eating and drinking, and other forms of oral stimulation (e.g. oral hygiene) 90 minutes prior to the collection of saliva. It is anticipated that the length of each patient's pre-radiotherapy dental assessment will be at least 90 minutes (based on current clinical practice). Patients will therefore be instructed not to engage in oral stimulation for 90 minutes after they have signed the written consent form at the start of the appointment.

-Ruler measurement of **mouth opening**. Maximum interincisal distance will be measured when the upper and lower central incisors are present (natural or prosthetic). Alternatively, the alveolar ridge(s) will be used as a reference point for measurement where no natural or prosthetic central incisors are present.

All of the above data, including the Oral Health Assessment Forms, will be recorded and stored in patients' clinical records (dental notes).

**-Oral hygiene practice and dietary assessments** will be performed using the World Health Organization's Oral Health Questionnaire for Adults.

**-Quality of life** and experience of **xerostomia** will be assessed using questionnaire booklets containing the European Organization for Research and Treatment of Cancer (EORTC) QLQC30 quality-of-life instrument, the associated head and neck specific module HN35, the Oral Health Impact Profile, and the modified Xerostomia Questionnaire.

**-Micro-costings study.** Patients will also be asked to complete a short questionnaire enquiring of their gross annual income, the mode of transport they used for attending their dental appointment, and whether another person accompanied them to their dental appointment. The micro-costings study questionnaire will be attached to the oral hygiene/diet/quality of life/xerostomia questionnaire booklet outlined above.

The questionnaire booklets will be completed anonymously. Upon acceptance into the study, a random number generator will assign each recruited patient a 6-digit anonymous code. Each patient will be informed of his or her anonymous code. This will be the only identifier recorded on completed questionnaire booklets.

Patients will be asked to complete the questionnaire booklet in one of the dental units in the main clinic of the School of Dentistry, Belfast. The questionnaire booklets will be given to, and collected by, the dentist performing the clinical assessments. They will be stored securely in a locked cupboard in a locked room in the School of Dentistry, Belfast.

A password-protected spreadsheet will be created with a list of patients' anonymous codes and their corresponding Dental Health and H&C numbers. This will be stored on a password-protected Belfast Health and Social Care Trust computer.

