#### **SPECIAL CASES**

Dental phobic patients – may consider additional extraction of any tooth with caries.

Impacted/unerupted teeth – extract when in communication with oral cavity, carious, or other pathology suspected (e.g. cyst formation, resorption of adjacent teeth).

Retained roots/apices – leave when no pathology and encased entirely within bone.

Patients deemed to have poor prognosis or to receive palliative treatment only – may limit number of extractions on this basis.

Dental neglect (toothbrushing <1x per day, intake of >5 sugar attacks per day, caries affecting >75% of remaining teeth) – may consider additional extraction of teeth or complete dental clearance.

Patients with oral cancer – additional teeth in close proximity to tumour may require removal as part of the oncology surgical approach.

Patients taking bisphosphonate medications – need to liaise with Oral Surgery or Maxillofacial Team.

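### The periodontal case rule counts diseased sites without regard to teeth present, and the periodontal logistic models have no term for tooth number, a likely outcome predictor that could bias the dose association in either direction

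*Combined protocol and SAP*

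**What the plan says.** Under Clinical assessment, pocket depth and attachment loss are "recorded for six sites on each tooth using the Oral Health Assessment Form". A case needs "2 or more interproximal sites with attachment loss" of at least 3 mm, "and 2 or more interproximal sites with pocket depths" of at least 4 mm on different teeth, "or one site with pocket depth" of at least 5 mm. I read this as the attachment-loss condition plus either pocket condition. No part of the rule is expressed per tooth or per site examined.

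The exclusion criteria set only a floor on tooth number: "Patients with less than 6 teeth before the radiotherapy start date".

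In Statistical analysis, item (2), case status is first compared across dose bands by chi-square. Then: "Adjusted analysis will be performed using logistic regression with presence of periodontal disease as the outcome variable". Parotid dose is the explanatory variable, with "dental radiation dose, oral hygiene practice, diet, smoking, medical history, and mouth opening as potential confounders". Similar analyses follow for dental dose and tumour location. Teeth present appear in none of these lists, and tooth loss appears only as a secondary outcome.

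The plan itself makes tooth number depend on other things. The pre-radiotherapy extraction table includes deep pockets, bone loss, furcation disease and mobility among its criteria. Special cases allows further extractions for dental neglect and, in oral cancer, says that "additional teeth in close proximity to tumour may require removal as part of the oncology surgical approach".

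**The concern.** A fixed count is easier to reach when more sites are probed. Two patients whose individual sites are equally likely to be diseased can therefore be classified differently because one has more teeth. If tooth number also varies with exposure, part of the dose contrast in a primary outcome reflects how many sites were available.

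For tumour location, a link to tooth number is written into Special cases. For dental dose, a link through tumour site is plausible but not documented. For parotid dose, the documents give no mechanism. If tooth number is unrelated to all three, leaving out a predictor of the outcome still pulls a logistic odds ratio towards 1 and costs precision.

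**Working it through.** **Inputs from the documents.** The case rule and six sites per tooth (Clinical assessment); a minimum of 6 teeth (Exclusion criteria); 150 patients with data and an 80%/20% split at 20 Gy to the spared parotid, i.e. 120 and 30 (Sample size). There is no planned figure to reproduce: Sample size deals with carious teeth only and gives no periodontal rate or power.

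**Assumptions.** Four of the six sites per tooth are interproximal, so 6 teeth give 24 interproximal sites and 28 teeth give 112. The upper figure of 28, all site prevalences and all tooth-number contrasts are assumed.

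**Step 1: does the rule depend on tooth number?** Take independent sites, 2% with pockets of at least 4 mm, and the two-site clause alone, ignoring the different-teeth condition. The chance of meeting it with n sites is 1 − 0.98^n − n × 0.02 × 0.98^(n−1):

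- n = 24: 1 − 0.616 − 0.302 = 8.3%
- n = 112: 1 − 0.104 − 0.238 = 65.8%

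Now require different teeth, add the single-site route, and assume attachment loss is present at these sites. For T teeth, P = 1 − [a^T + T × a^(T−1) × (b − a)], where a = (1 − q4)^4 and b = (1 − q5)^4. With q4 = 0.02 and q5 = 0.004, a = 0.9224 and b = 0.9841, so P is 13.7% at 6 teeth and 70.1% at 28. The single-site route softens the dependence but does not remove it.

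Independent sites exaggerate the gap. With patient-level risk following a beta distribution and intra-patient correlation 0.1, the same 2% gives 12.6% at 6 teeth and 29.7% at 28.

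**Step 2: a moderate contrast with no true dose effect.** The full rule was simulated with a patient random effect on the logit scale. Assumptions: 1–5% of interproximal sites with pockets of at least 4 mm, 0.2–1% of all sites at least 5 mm, and 10–25% of interproximal sites with attachment loss of at least 3 mm. Per-site disease is the same at every tooth number.

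| Pockets ≥4 mm, SD | 6 teeth | 16 teeth | 20 teeth | 28 teeth | OR, 16 vs 20 |
|---|---|---|---|---|---|
| 1%, 1.0 | 0.075 | 0.238 | 0.289 | 0.381 | 0.77 |
| 2%, 1.0 | 0.170 | 0.420 | 0.486 | 0.589 | 0.77 |
| 2%, 1.5 | 0.146 | 0.316 | 0.362 | 0.438 | 0.81 |
| 5%, 1.5 | 0.315 | 0.546 | 0.592 | 0.674 | 0.83 |
| 5%, 2.0 | 0.253 | 0.424 | 0.469 | 0.532 | 0.83 |

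Each odds ratio comes from its row; the first is (0.238/0.762)/(0.289/0.711) = 0.77. Repeating the simulation gives about 0.76 to 0.84. A wider contrast of 14 versus 22 teeth gives 0.56 to 0.70.

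**Step 3: relax equal per-site disease.** If site-level odds of disease are about 1.25 times higher in the fewer-teeth group, the 16-versus-20 effect disappears in all five settings. About 1.5 to 1.75 cancels 14 versus 22. Beyond that the sign reverses.

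**Step 4: direction and the effect of adjusting.** Logistic simulations used 150 patients split 120/30, 2% site risk, intra-patient correlation 0.1 and 600 runs per scenario. The odds ratios are for high versus low dose, without and with log(teeth) in the model.

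| Mean teeth, low / high dose | No dose effect: without, with | Site-level dose OR 2: without, with |
|---|---|---|
| 22 / 16 | 0.82, 1.02 | 1.95, 2.48 |
| 16 / 22 | 1.25, 1.05 | 2.94, 2.39 |
| 18 / 18 | 1.05, 1.04 | 2.46, 2.51 |

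Fewer teeth at high dose shrinks the estimate, more teeth inflates it, and no difference leaves slight attenuation.

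**Step 5: scale against sampling error.** For the 30/120 split, SE(log OR) = √[(1/30 + 1/120)/(p(1 − p))]. This is 0.47 at p = 0.25 and 0.41 at p = 0.50. The 16-versus-20 shift is |ln 0.76| = 0.27 to |ln 0.84| = 0.17, or roughly half a standard error.

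**The case against.** A reader might infer that patients with fewer teeth are much less likely to be called cases, and that a harmful dose effect is therefore hidden. The documents do not support this, for three reasons.

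First, it needs equal per-site disease at every tooth number. The extraction criteria and the dental-neglect provision make a low tooth count partly a marker of past periodontal disease and poor hygiene, which could raise the risk at the remaining sites. Removing diseased teeth could equally leave healthier ones. Step 3 shows that a modest difference is enough to cancel the effect.

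Second, no tooth-number distribution is given, and nothing ties tooth number to parotid dose. For dental dose, losing teeth beside the tumour could lower the mean dose to those that remain. That would pair fewer teeth with lower dose, the opposite of hiding an effect.

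Third, the hypothesis concerns the proportion of patients with disease. The rule is a cited person-level definition applied to full-mouth charting, so a patient who meets it does have the diseased sites. The definition is legitimate, and the 6-versus-28 comparison contrasts extremes.

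All three points limit the claim on direction and size. None removes the omission: tooth number is likely to be prognostic by one route or the other, and the models leave it out.

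**Conclusion.** The point holds as an omitted covariate in the models for one of the two primary outcomes. The fixed-count rule and the missing term are plain in the text. It follows by arithmetic that, at equal per-site disease, more teeth means a higher chance of being a case.

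Bias additionally requires tooth number to differ by dental dose, parotid dose or tumour location, and it can then run either way. Without such a difference, the cost is attenuation or lost precision. The spurious odds ratio of about 0.76 to 0.84 for 16 versus 20 teeth rests on assumed prevalences, an assumed contrast and equal per-site disease. It illustrates the possible size and is not an estimate for this cohort. The change is worth making because it is cheap and covers both directions, not because a hidden effect has been shown.

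**What to change.** In Statistical analysis, item (2), add the number of teeth present at the start of radiotherapy to the periodontal logistic models for parotid dose, dental dose and tumour location. It is the baseline chart less the pre-radiotherapy extractions. Report tooth number by dose band beside the chi-square comparison, so that readers can see whether it is related to exposure. Keep the cited case definition.

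Do not adjust for teeth present at 24 months, since tooth loss by then may result from dose. The pre-radiotherapy count precedes exposure and cannot be a mediator.

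The cost is a line of wording and one degree of freedom with about 150 patients; the tooth charting is already planned. Two limits remain. The term adjusts for sites at risk and prior susceptibility together and cannot separate them. It also does not deal with diseased teeth removed during follow-up, which leave the 24-month chart; the plan should state how those are counted.
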